7.8 Serious Adverse Events (SAEs)

All SAEs must be recorded on the SAE CRF and be faxed immediately to the CTRU. See section 8 for further details.

7.9 Deaths

Death must be recorded on the Death Form. The date and cause of death will be collected. Death forms must be returned to CTRU within 7 days of the death being notified to the site team.

7.10 Quality of Life questionnaires

Quality of Life data will be collected in clinic prior to randomisation and via postal questionnaires at 12 and 24 weeks post-randomisation using the EORTC QLQ-C30, EQ-5D, Dermatology Life Quality Index (DLQI) and the MRC treatment value/acceptability supplement. To maintain confidentiality, patients will be provided in clinic with envelopes in which to seal their completed questionnaires. The CTRU will collect patients' full name and address on an individual Contact Details CRF in order to send out postal questionnaires. Prior to sending out postal questionnaires, the CTRU will confirm the patient's status and address with the hospital staff responsible for their care. Stamped addressed envelopes will be provided with the postal questionnaires. If a patient does not return the completed questionnaire within 2 weeks of posting one reminder questionnaire will be sent. If the patient does not respond to the reminder letter it will be deemed that the patient does not wish to complete the questionnaire. On receipt of a completed questionnaire the CTRU will post a letter of thanks to the patient.

7.11 Definition of End of Trial

The end of the trial is defined as the date of the last visit of the last patient undergoing the protocol based drug therapy. Follow-up will continue for one year after the last patient is randomised.

7.12 PK sub-study

In centres with appropriate facilities a subset of 20 patients will participate in the pharmacokinetic (PK) Sub-study (see Appendix 4). If a patient has consented to participate, ten 7ml blood samples will be collected prior to starting treatment, at 7 time points during the 6 hours following treatment and at 24 and 48 hours after treatment. The blood should be separated and the plasma stored at -40°C. The CTRU will arrange for the samples to be transported to the analysis laboratory. A contribution to PK sampling costs will be available (please contact CTRU for details).

8. PHARMACOVIGILANCE PROCEDURES

Within the trial, the following are defined as Investigational Medicinal Products (IMPs): irinotecan, ciclosporin and panitumumab.

8.1 General definitions

8.1.1 Adverse events

An adverse event (AE) is any untoward medical occurrence in a patient or clinical trial subject which does not necessarily have a causal relationship with this treatment and can include:

- any unintentional, unfavourable clinical sign or symptom
- any new illness or disease or the deterioration of existing disease or illness
- any clinically relevant deterioration in any laboratory assessments or clinical tests

8.1.2 Serious adverse events

A serious adverse event (SAE) is defined in general as any untoward medical occurrence or effect which:

- is fatal or life threatening*
- requires or prolongs hospitalisation
- is significantly or permanently disabling or incapacitating
- constitutes a congenital anomaly or a birth defect or
- may jeopardise the patient and may require medical or surgical intervention to prevent one of the outcomes listed above

* the term life threatening refers to an event in which the patient was at risk of death at the time of the event; it does not refer to an event which hypothetically might have caused death if it was more severe.

Where an SAE is deemed to have been related to an IMP used within this trial the event is termed a Serious Adverse Reaction (SAR).

8.1.3 Suspected unexpected serious adverse reactions

A suspected unexpected serious adverse reaction (SUSAR) is a serious adverse drug reaction which also demonstrates the following characteristic of being unexpected:

Unexpected – An adverse event, the nature OR severity of which is NOT consistent with the applicable product information (e.g. Investigator's Brochure for an unapproved investigational medicinal product, Summary of Product Characteristics for a marketed product).

8.2 Operational definition and reporting adverse events

From the first administration of trial treatment until 3 weeks after the last trial drug administration, all toxicities related to the underlying colorectal cancer or its treatment, whether observed by the investigator or reported by the patient, will be collected and recorded on a Case Report Form (CRF) following each cycle of treatment. The CTRU will provide details of all toxicities to the Data Monitoring and Ethics Committee (DMEC) for their review on a yearly basis.

Specifically, known toxicities associated with irinotecan, ciclosporin and panitumumab, as identified from the most recent Summary of Product Characteristics for irinotecan and ciclosporin, and the most recent panitumumab Investigator Brochure will be collected. The following will therefore be included:

- Diarrhoea
- Nausea
- Vomiting
- Constipation
- Headache
- Lethargy
- Alopecia
- Dizziness
- Skin toxicity
- Abdominal pain
- Pyrexia
- Anaemia
- Neutropenia

- Thrombocytopenia
- Infection
- Nail toxicity
- Plus any other reported side-effects following each cycle of treatment of CTC grade ≥ 3

The following infusion related toxicities will also be collected:

- Fever
- Chills
- Respiratory
- Bradycardia/cardiac arrest
- Generalised urticaria
- Diarrhoea
- Arthralgia/myalgia
- Rigors/shakes
- Hypotension
- Plus any other reported infusion related toxicities following each cycle of treatment CTC grade ≥ 2

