3. TRIAL DESIGN

PICCOLO is a multi-centre, open-label, randomised, controlled, 4 arm clinical trial designed to show whether, regardless of tumour subtype, the novel regimen **IrCs**, is non-inferior for anti-cancer efficacy and superior for toxicity compared to **Ir**, and whether, in patients with *K-RAS* wild-type tumours, the addition of panitumumab to irinotecan, **IrPan**, gives superior anti-cancer efficacy compared to **Ir** alone.

Potential PICCOLO patients are invited to consent to retrieval of stored tumour samples to test for *K-RAS* mutations at codons 12, 13 and 61. Thereafter, patients who fulfil the eligibility criteria and give informed consent are randomised according to their tumour *K-RAS* status as shown in the flow diagram on page 5.

Patients whose tumours are shown to have a mutation in *K-RAS*, and those in whom *K-RAS* genotyping is not possible due to assay failure or unavailability of tissue, are allocated on a 1:1 random basis to receive **Ir** or **IrCs**. This randomisation uses the minimisation factors listed in the flow diagram.

Patients whose tumours are wild-type for *K-RAS* are allocated on a 1:1 random basis to receive **Ir** or **IrPan**. This randomisation is stratified according to whether or not the patient has received prior anti-EGFR targeted therapy (e.g. cetuximab or panitumumab), and uses the minimisation factors listed in the flow diagram.

Recruitment to PICCOLO will continue until 480 non-EGFR-pre-treated *K-RAS* wild-type patients have entered the **Ir** vs. **IrPan** randomisation (240 patients per arm), and 750 patients have entered the **Ir** vs. **IrCs** randomisation (375 patients per arm). The **Ir** vs. **IrPan** comparison includes approximately 143 patients fulfilling these criteria who were randomly allocated to **Ir** or **IrPan** under Protocol Version 1 (in whom *K-RAS* status is being determined retrospectively), plus approximately 337 patients to be recruited using Protocol Version 2. The **Ir** vs. **IrCs** comparison includes 329 patients randomly allocated to **Ir** or **IrCs** under Protocol Version 1 (regardless of their *K-RAS* status), plus approximately 421 patients to be recruited using Protocol Version 2. The recruitment ratio to the **Ir** vs. **IrCs** comparison and the **Ir** vs. **IrPan** comparison is dependent upon the proportion of patients with unknown *K-RAS* status (which we

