7.5 Treatment Assessments

Patients will be assessed clinically for symptoms and toxicity at the start of each drug therapy cycle i.e. 3-weekly. The CRF completed at these visits will include specific questions about the expected side-effects of the study drugs (using NCI-CTC version 3), plus any additional side effects, during the preceding cycle. Serious adverse events will be reported according to the Medicines for Human Use (Clinical Trials) Regulations 2004 (see section 8). On Day 1 of treatment (day of irinotecan infusion) the following investigations and assessments will be carried out:

- Height, weight, body surface area and WHO performance status (may be assessed up to 5 days prior to Day 1)
- Laboratory tests including FBC, LFTs, U&Es, magnesium and calcium (may be assessed up to 5 days prior to Day 1)
- Toxicity relating to the previous cycle assessed by NCI-CTC[V3] grades

In addition the following data will be collected:

- Cycle details including dose given, dose alteration/delay and reason

N.B. When a patient permanently stops trial treatment please fax a copy of the completed Treatment Stop Fax (section 7 of the Investigator Site File) to the CTRU.

7.6 12-Week Reassessment

At 12 weeks post-randomisation the following investigations and assessments will be carried out:

- Reassessment CT scan and response by RECIST criteria
- Toxicity assessed by NCI-CTC[V3] grades

In addition the following data will be collected:

- Clinical evidence of disease progression or not
- Treatment plan (i.e. continue or stop treatment)
- Details of any non-trial anti-cancer treatment received since randomisation
- Quality of Life questionnaires (for details please refer to section 7.9)

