10.2 Secondary Endpoints

Ir vs IrCs comparison

- Proportion of patients free from treatment failure at 12 weeks
- Overall survival (OS) from randomisation
- Research nurse-assessed toxicity (NCI-CTC[V3] grades): maximum toxicity grade per patient; rate per cycle; all-cause mortality within 60 days of randomisation; toxicity of primary interest is grade 3+ diarrhoea within 12 weeks of randomisation;

Ir vs IrPan comparison (patients with wild-type K-RAS status not previously receiving an anti-EGFR targeted therapy)

- Proportion of patients progression-free 12 weeks from randomisation.
- Research nurse-assessed toxicity (NCI-CTC[V3] grades): maximum toxicity grade per patient; rate per cycle; all-cause mortality within 60 days of randomisation;

Ir vs IrCs and Ir vs IrPan (patients with wild-type K-RAS status not previously receiving an anti-EGFR targeted therapy) comparisons

- Progression-free survival (PFS) from randomisation
- Best response by RECIST criteria within 1-year follow-up from randomisation
- Patient-assessed symptom/QL/PA scores at 12 and 24 weeks

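### The opening rule of 8.2 ties toxicity recording to the cancer or its treatment, against the cause-free definition in 8.1.1, so in this open-label trial events put down to a third cause can go unrecorded, mainly unlisted grade 3 or higher events

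*Protocol*

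**What the plan says.** - **General definition (8.1.1).** An adverse event is an untoward occurrence "which does not necessarily have a causal relationship with this treatment".
- **Operational rule (8.2).** From first treatment until three weeks after the last dose, the CRF collects "all toxicities related to the underlying colorectal cancer or its treatment, whether observed by the investigator or reported by the patient". The next paragraph begins "Specifically, known toxicities associated with irinotecan, ciclosporin and panitumumab" and says these will be collected. It gives a list with diarrhoea first, ending with a catch-all for other reported side-effects of grade 3 or higher.
- **Cycle visits (7.5).** The CRF has "specific questions about the expected side-effects of the study drugs (using NCI-CTC version 3), plus any additional side effects, during the preceding cycle". Section 7.6 has toxicity graded by CTC again at 12 weeks.
- **Endpoint (10.2).** For Ir versus IrCs, the "toxicity of primary interest is grade 3+ diarrhoea within 12 weeks of randomisation". Section 12 tests it with a two-sided chi-squared test. Neither place mentions relatedness.
- **Safety presentation (12).** Events are shown by relationship to study drug or to the underlying cancer. No other category is named.
- **Blinding (3).** "PICCOLO is a multi-centre, open-label, randomised, controlled, 4 arm clinical trial".

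**The concern.** The protocol defines adverse events without regard to cause and then collects toxicities by cause. Relatedness works as a condition of entry to the dataset when it should be a descriptor of events already in it. An event that the site attributes to something other than the cancer or its treatment (diet, an unrelated illness, a late effect of earlier radiotherapy) falls outside the opening sentence of 8.2. The two relationship categories in section 12 match that scope, so such an event has no place in the tables either.

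Because the trial is open-label, the attribution is made by people who know the arm, and the rate at which events drop out could differ between arms. A non-serious event left off the CRF for this reason cannot be restored at analysis by reclassifying it. At stake are the completeness of the toxicity profile in all arms and the maximum-grade and per-cycle summaries in 10.2. To a much smaller degree, so is the grade 3+ diarrhoea comparison, which is the leading tolerability measure for IrCs.

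**Working it through.** **Which events can the wording remove?**

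1. *Events due to the cancer rather than the drug:* none. The 8.2 phrase admits both, so choosing between them removes nothing. Only a third cause takes an event outside it.
2. *Listed toxicities, including diarrhoea:* doubtful. The list is drawn up by type of toxicity from product information, and 8.2 states no case-by-case judgement. Section 7.5 asks about expected side-effects each cycle. Appendix 2 defines grade 3 diarrhoea by stool count, incontinence, intravenous fluids or hospitalisation, not by cause. However, the list opens as a specification of the sentence before it, and nothing says the toxicities are recorded regardless of cause. The text is ambiguous, and the natural reading is that all are collected.
3. *Serious events:* none. Section 8.1.2 counts hospitalisation as serious whatever the cause, and 8.4 collects all SAEs to 30 days after last treatment with causality as a separate field.
4. *Unlisted, non-serious events of grade 3 or higher:* exposed. The catch-all is itself worded as side-effects and sits under the relatedness sentence.

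**The plan's own figure for diarrhoea**

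Inputs from section 11.1: 375 per arm, 20% on Ir, 10% on IrCs, two-sided 5% chi-squared test without continuity correction.

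Probability of a significant result favouring IrCs = Φ[(p1 − p2 − 1.96·SE0)/SE1], where SE0 = √(2p̄(1−p̄)/n), SE1 = √([p1(1−p1) + p2(1−p2)]/n) and p̄ is the mean of p1 and p2.

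- SE0 = √(2 × 0.15 × 0.85/375) = 0.02608, and 1.96 × SE0 = 0.05111.
- SE1 = √((0.16 + 0.09)/375) = 0.02582.
- (0.10 − 0.05111)/0.02582 = 1.89, so power is 97.1%.

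With 340 per arm (the 680 before allowance for drop-out) it is 95.6%. Both agree with the stated figure of over 90%.

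**Illustration of differential omission (assumed rates)**

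Take a true 20% in both arms, about 75 of 375 patients each. A share q of IrCs cases goes unrecorded and none on Ir. The nominal error in this direction is 2.5%.

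- q = 10% (7 or 8 patients), recorded 20% v 18%: SE0 = 0.02865, SE1 = 0.02864; (0.02 − 0.05615)/0.02864 = −1.26; probability 10.3%.
- q = 20% (15 patients), recorded 20% v 16%: SE0 = 0.02806, SE1 = 0.02802; (0.04 − 0.05499)/0.02802 = −0.535; probability 29.6%.
- The same formula gives about 5% at q = 5% and 59% at q = 30%.

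**Equal omission in both arms**

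With true rates of 20% v 10% and the same share lost in each arm, power is 96.2%, 95.2% and 92.2% for losses of 5%, 10% and 20%. Only a loss that differs by arm would matter.

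**The case against.** A reader might infer that unblinded attribution decides whether grade 3+ diarrhoea is counted, and hence that the IrCs toxicity claim is biased. The documents do not support that. Diarrhoea heads the 8.2 list, is covered by the solicited cycle questions and is graded again at 12 weeks. Its grade does not depend on cause, and neither the endpoint nor its test carries a relatedness condition. The expected-events table in section 8.7 lists diarrhoea for both irinotecan and ciclosporin, and infection, an obvious alternative explanation, is itself a listed toxicity. Section 6.4 directs admission for prolonged diarrhoea or symptoms of dehydration, so many such episodes also reach the SAE system. Cycle CRFs record dose changes with reasons, and source data verification is provided for in 13.2, so some omissions could be detected. The false-positive figures need sizeable one-sided omission of a solicited item, for which the documents give no basis.

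Most of this stands, and it confines the point. Three things survive. The 8.2 sentence conflicts with 8.1.1. No sentence lifts the condition for listed items. The SAE route does not reach every grade 3 episode, since a rise of seven or more stools a day, or incontinence, qualifies without admission. For unlisted non-serious events the objection offers little beyond the general request in 7.5 for any additional side effects.

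General bias in open-label grading is a separate matter, which this change would not cure.

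**Conclusion.** The point holds as a defect of wording with a limited practical reach. The opening rule of 8.2 contradicts 8.1.1 and permits events attributed to a third cause to go unrecorded in an open-label trial. The main effect is on unlisted, non-serious events of grade 3 or higher. For diarrhoea and the other listed toxicities the text is ambiguous but most naturally read as collecting everything. The finding is that the wording permits filtering, not that filtering occurs.

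The stated power for diarrhoea is sound and unaffected. The figures of about 10% and 30% show only what assumed losses of 10% and 20%, confined to IrCs and with no true difference, would do. They are not estimates of bias in this trial.

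**What to change.** - In 8.2, delete the relatedness condition. State that the CTC grade of every listed toxicity, including diarrhoea, and of any other event of grade 3 or higher is recorded whatever its attributed cause.
- Keep relationship as a separate CRF field, add an unrelated/other category, and carry that category into the safety presentation in section 12.
- State in section 12 that the grade 3+ diarrhoea comparison uses all-cause grades.

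The cost is a few sentences and a CRF instruction with one added response category. The downside is a few more unrelated events on the CRF. Sample size and test are unchanged.

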8.2.1 Pre-existing conditions

A pre-existing condition must not be reported as an AE unless the condition worsens significantly during the trial treatment.

8.2.2 Diagnostic and surgical procedures

Diagnostic and therapeutic non-invasive and invasive procedures, such as surgery, must not be reported as an AE. The medical condition for which the procedure was performed must be reported.

8.3 Operational definition serious adverse events (SAEs)

Death as a result of disease progression does NOT require reporting as an SAE, the Death Form should be completed and returned to the CTRU.

In addition, events NOT considered to be serious adverse events are hospitalisations for:

- routine treatment or monitoring of the studied indication, not associated with any deterioration in condition
- treatment, which was elective or pre-planned, for a pre-existing condition that is unrelated to the indication under study, and did not worsen
- admission to a hospital or other institution for general care, not associated with any deterioration in condition
- treatment on an emergency, outpatient basis for an event not fulfilling any of the definitions of serious given above and not resulting in hospital admission

8.4 Reporting serious adverse events

SAEs will be collected for all patients from the first trial treatment to 30 days after the last trial treatment. All SAEs must be recorded on the Serious Adverse Event Form and faxed to the CTRU on [name] within 24 hours of the research staff becoming aware of the event.

The local investigator must assign causality and expectedness to the SAE. A nominated individual at the CTRU will be responsible for the SAE procedures within the trial.

For each SAE, the following information will be collected:

- full details in medical terms with a diagnosis, if possible
- its duration (start and end dates; times, if applicable)
- action taken
- outcome
- causality, in the opinion of the investigator*
- whether the event would be considered expected or unexpected* (refer to the most recent and relevant Summary of Product Characteristics or Investigator Brochure)

*Assessment of causality and expectedness must be made by an authorised doctor. If an authorised doctor is unavailable, initial reports without causality and expectedness assessment should be submitted to the CTRU by a healthcare professional within 24 hours, but must be followed up by medical assessment as soon as possible thereafter. Please also indicate on the fax cover sheet when a medical assessment will be provided.

The local investigator and others responsible for patient care should institute any supplementary investigations of SAEs based on their clinical judgement of the likely causative factors. This may include seeking a further opinion from a specialist in the field of the SAE. If a patient dies, any post-mortem findings including histopathology must be provided to the CTRU. The CTRU will report all deaths to the DMEC for continuous safety review.

SAEs still present at the end of the study must be followed up at least until the final outcome is determined, even if it implies that the follow-up continues after the patient finishes the study treatment and when appropriate until the end of the planned period of follow-up.

The CTRU will inform the owner of panitumumab (Amgen Inc.) of all SAEs relating to patients on the IrPan arm within 1 working day of receipt, regardless of whether the event is suspected to be related to irinotecan or panitumumab.

The CTRU will report all SAEs to the main REC annually. All SAEs will also be reported to the DMEC for review approximately every three months to determine patterns and trends of events or identify safety issues.

The Investigator is responsible for reporting SAEs to their host institution, according to local regulations.

The Investigator does not need to inform the MHRA of SAEs related to the study drugs and expected, as this will be done annually by the CTRU. All adverse drug reactions suspected to be related to other licensed drugs used in standard care, for example anti-emetics, should be reported by the local investigator using the yellow card system. In agreeing to the provisions of this protocol, these responsibilities are accepted by the Investigator.

8.5 Reporting suspected unexpected serious adverse reactions (SUSARs)

All SAEs assigned by the local investigator as both *suspected* to be related to the trial drugs and *unexpected* are subject to expedited reporting. An event is unexpected when information is not consistent with the available product information or if they add significant information on the specificity or severity of an expected reaction (see Section 8.6).

The Chief Investigator (CI) or nominated individual will undertake urgent review of SUSARs within 24 hours of reporting and may request further information immediately from the patient's clinical team. The CI should not overrule the causality, expectedness or seriousness assessment given by the local investigator but may comment on these. The Investigator does not need to inform the MHRA of SUSARs. The CTRU will report all SUSARs to the MHRA and the main REC, within 7 days of the initial report being received, if the SUSAR resulted in death or was life-threatening, or within 15 days for any other unexpected serious adverse reaction. It is also recommended that the CTRU report all SUSARs related to irinotecan or ciclosporin to the marketing authorisation holders.

If information is incomplete at the time of initial reporting, the CTRU will request follow-up information, including information for analysis of causality, from the local investigator and will send the follow-up information to the MHRA and main REC within an additional 8 days for fatal or life-threatening SUSARs and as soon as possible for any others.

The CTRU will inform the owner of panitumumab (Amgen Inc.) of all SAEs relating to patients on the IrPan arm within 1 working day of receipt, regardless of whether the event is suspected to be related to irinotecan or panitumumab. Amgen will undertake urgent review of SUSARs and may request further information from the patient's clinical team via CTRU.

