8.7 Pharmacovigilance responsibilities

Local investigator:

1. Medical judgement in assigning to AEs:
 - Seriousness
 - Causality
 - Expectedness
2. To fax SAE form to CTRU within 24 hours of becoming aware and to provide further follow-up information as soon as available
3. To report SAEs to local committees in line with local arrangements

Chief Investigator (or nominated individual in CI's absence):

1. Chief Investigator to assign causality and expected nature of SAEs where it has not been possible to obtain local assessment
2. Chief Investigator will review all events assessed as SAEs in the opinion of the local investigator
3. Chief Investigator to review all events assessed as SUSARs in the opinion of the local investigator. In the event of disagreement between local assessment and Chief Investigator review with regards to SUSAR status, local assessment will not be overruled, but Chief Investigator may add comments prior to reporting to MHRA.

CTRU:

1. Report SAEs relating to patients on the IrPan arm to Amgen within 1 working day
2. Expedited reporting of SUSARs to MHRA and main REC within required timelines
3. Preparing annual safety reports to MHRA and main REC
4. Preparing safety reports for the DMEC at 3-monthly intervals for SAEs
5. Notifying Investigators of SUSARs which compromise patient safety
6. Distributing CIOMs line listings, as provided by Amgen quarterly, to Investigators and main REC on a regular basis

TSC:

1. Role in reviewing safety data and liaising with the DMEC regarding safety issues, as required

DMEC:

1. 3-monthly review of unblinded overall safety data to determine patterns and trends of events, or to identify safety issues, which would not be apparent on an individual case basis
2. Review of interim analysis

AMGEN INC:

1. Reporting all SUSARs related to panitumumab to the Global Regulatory Authorities, except to MHRA, within the required timelines
2. Providing the CTRU with quarterly Investigator CIOMs line listings
3. Review all SAEs relating to patients on the IrPan arm and inform CTRU of any upgrades to SUSAR

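### On Ir and IrCs, sections 8.5 and 8.7 give no one a stated power to upgrade a site's completed SAE assessment to SUSAR, and section 8.5 does not say what follows a manufacturer upgrade on IrPan

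*Protocol*

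**What the plan says.** Section 8.5 sets the trigger for expedited reporting on all arms: "All SAEs assigned by the local investigator as both *suspected* to be related to the trial drugs and *unexpected* are subject to expedited reporting". It then describes the Chief Investigator's urgent review of SUSARs within 24 hours and limits that role: "The CI should not overrule the causality, expectedness or seriousness assessment given by the local investigator but may comment on these".

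Section 8.7 (Pharmacovigilance responsibilities) lists three tasks for the Chief Investigator:

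- filling gaps: "Chief Investigator to assign causality and expected nature of SAEs where it has not been possible to obtain local assessment";
- reviewing every SAE: "Chief Investigator will review all events assessed as SAEs in the opinion of the local investigator";
- reviewing events that the site has called SUSARs, where on disagreement "local assessment will not be overruled, but Chief Investigator may add comments prior to reporting to MHRA".

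For IrPan there is a further reviewer. Under section 8.4 the CTRU informs the manufacturer "of all SAEs relating to patients on the IrPan arm within 1 working day of receipt", whichever drug is suspected. Section 8.7 then gives the manufacturer this task: "Review all SAEs relating to patients on the IrPan arm and inform CTRU of any upgrades to SUSAR". No counterpart is named for Ir or IrCs.

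**The concern.** The usual purpose of central SAE review is to catch an event that a site has classified too leniently. Here the Chief Investigator sees every SAE on every arm, but no sentence says that a more cautious central view has any effect once the site has completed its assessment. Only the manufacturer has a stated upgrade role, and only for IrPan.

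What is at stake is the speed of reporting. Under section 8.5 a SUSAR goes to the MHRA and the main REC within 7 days if it was fatal or life-threatening, and within 15 days otherwise. Under section 8.4 an SAE without that status is covered by the annual report to the main REC and the roughly three-monthly DMEC review.

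The gap matters most for IrCs, planned at 375 patients. Ciclosporin is given there to change irinotecan handling (section 1 reports AUCs raised about 2.3-fold). Section 8.7 (Expected SAEs for specific drugs/treatments) lists expected events drug by drug and sends the reader to the SPC for interactions. Deciding whether an event's severity goes beyond the label is then a real judgement, and sites can differ on it.

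**Working it through.** The protocol states no figure on this point, so the check is to follow one type of event through the rules: an SAE with a completed site assessment of expected or unrelated, where a central reviewer thinks it is a SUSAR.

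| Step | Ir and IrCs | IrPan |
|---|---|---|
| Site classification triggers expediting (8.5)? | No | No |
| Chief Investigator sees the event (8.7)? | Yes | Yes |
| Chief Investigator has a stated power to upgrade? | None | None |
| Chief Investigator may assign the classification? | Only if the local assessment could not be obtained | Same |
| Another reviewer with a stated upgrade role (8.7)? | None | Manufacturer |
| CTRU action after an upgrade stated in 8.5? | Not applicable | No |

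Four points follow.

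1. **Trigger.** For a completed site assessment, section 8.5 names one trigger, the local investigator's own assignment. Nothing else in 8.5 or 8.7 starts expedited reporting on Ir or IrCs.

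2. **Scope of the no-overrule rule.** In section 8.7 the clause belongs to the item on events the site has already called SUSARs, where the only possible change is downward. In section 8.5 the sentence follows the SUSAR review, but it names causality, expectedness and seriousness in general and gives no direction. A reader could take it either way. On the narrow reading upgrades are not forbidden, but they are still not provided for.

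3. **Other routes.** Assigning a missing assessment fills a gap and does not correct a completed one. A site may revise its view after a comment, but nothing requires this and no time limit is set. The DMEC's task is a "3-monthly review of unblinded overall safety data to determine patterns and trends of events"; it has no stated role in reclassifying single events, and its interval is far longer than 7 or 15 days.

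4. **Manufacturer upgrade.** Section 8.7 has the manufacturer report panitumumab-related SUSARs to regulators other than the MHRA. Reporting to the MHRA therefore falls to the CTRU. Section 8.5 ties that reporting to the site's assignment and counts the 7 or 15 days from receipt of the initial report. It says neither that an upgrade counts as a trigger nor when the clock starts for an upgraded event.

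**The case against.** The strongest defence is that the no-overrule wording protects against a central reviewer removing a site's SUSAR. That is a sound safeguard, and the setting in both sections supports it. The separate duty to review all SAEs carries no such bar. This stands in part: the protocol is ambiguous on upgrades and cannot be said to prohibit them outright. It does not remove the gap, because no sentence supplies the power or makes the Chief Investigator's view count.

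It can also be said that section 8.1.3 defines a SUSAR by product information, not by who assigns it, and that the CTRU reports all SUSARs. This helps a manufacturer upgrade on IrPan, but it still names no one who decides on Ir or IrCs. Sections 8.5 and 8.6 require an event to be called unexpected when its severity departs from the label, which partly covers altered exposure on IrCs. That rule, however, is still applied by the site.

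A reader might go further and infer that SUSAR counts are inflated on IrPan by some calculable percentage, or that the DMEC's comparison of safety between arms is compromised. The documents do not support this. They give neither a rate of site misclassification nor a rate of upgrading, so any percentage would rest on invented inputs. SUSAR counts are not an endpoint and no comparison of them is planned. Section 10 uses graded toxicity, grade 3+ diarrhoea and 60-day mortality, none of which depends on SUSAR status. Under section 8.4 the DMEC receives all deaths continuously and all SAEs about every three months, whatever their SUSAR status.

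Finally, giving the Chief Investigator an upgrade power does not equalise review across arms: IrPan would have three assessors and the others two. This is correct, and it is why the classifications should be stored separately.

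**Conclusion.** The point holds as a gap in the safety-reporting rules. Followed as written, an Ir or IrCs event that the site calls expected or unrelated is not expedited, even if the Chief Investigator disagrees, unless the site revises its view. On IrPan an upgrade role exists, but its consequence for CTRU reporting is not stated.

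The number of events affected is unknown and cannot be derived from the protocol. For a single affected event the consequence is definite: reporting moves from 7 or 15 days to the routine cycle.

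The effect on analysis is minor and conditional. Section 12 tabulates safety data by arm and by relationship to study drug. If a manufacturer's revised causality were written over the site's, those tables would rest on different standards by arm; the protocol does not say whether this would happen.

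The conclusion rests on the text of sections 8.4 to 8.7 alone. A CTRU operating procedure could already close the gap, but section 8.5 would still need to agree with it.

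**What to change.** In section 8.5 and section 8.7 (Pharmacovigilance responsibilities), state that:

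- on every arm the Chief Investigator, acting for the sponsor, may upgrade but not downgrade causality, expectedness or seriousness;
- an upgrade by the Chief Investigator or by the manufacturer triggers expedited reporting by the CTRU to the MHRA and the main REC, with the start of the 7- or 15-day clock defined for upgraded events;
- local and final classifications are kept as separate variables, so that safety tables by relationship to study drug can use the site assessment on all arms.

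This needs a few sentences and one extra database field for each classification. The Chief Investigator already reviews every SAE, so no new review step is added. The downside is a few more expedited reports.
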